5.1.1 Neutropenia

Patients who experience neutropenia that causes a delay of ≥ 14 days between treatment cycles in the absence of other toxicity requiring dose modification should have the temozolomide dose reduced by 25% for subsequent cycles (see dose reduction nomogram in [Appendix IX](#)). If patient experiences neutropenia that causes a delay of ≥ 14 days between treatment cycles despite this dose reduction, protocol therapy must be discontinued and patient must be removed from protocol therapy.

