5.1.2 Thrombocytopenia

For patients who experience thrombocytopenia that causes a delay of ≥ 14 days between treatment cycles with or without other hematologic toxicities, the dose of temozolomide should be reduced by 25% for subsequent cycles (see dose reduction nomogram in [Appendix IX](#)). If patient experiences thrombocytopenia that causes a delay of ≥ 14 days between treatment cycles despite this dose reduction, protocol therapy must be discontinued.

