5.2.1 Dose Modifications for Diarrhea

See [Appendix V](#) for patient/family instructions for supportive care measures for patients who develop therapy-associated diarrhea. Also included are specific instructions for loperamide dosing.

- If Grade 4 therapy-associated diarrhea is experienced by a patient with no evidence of infectious etiology and despite maximal use of anti-diarrheal medications ([Appendix V](#)) and appropriate use of prophylactic antibiotics

([Section 4.2.1](#)), the dose of irinotecan should be reduced by 25% for subsequent cycles (i.e., irinotecan dose 37.5 mg/m²/dose for patients with BSA ≥ 0.6 m²).

- If Grade 4 therapy-associated diarrhea recurs without an infectious etiology despite reducing the dose of irinotecan by 25%, the dinutuximab dose should also be decreased by 25% for subsequent cycles (i.e. dinutuximab dose 13 mg/m²/day).
- If Grade 4 diarrhea recurs despite maximal use of anti-diarrheals, prophylactic antibiotics, and these dose reductions, the patient must come off protocol therapy.

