5.2.9 Other Non-Hematologic Toxicities

The above sections cover dose modifications for most anticipated adverse events with this regimen. For Grade 3 or higher non-hematologic toxicities not specified above or for non-hematologic toxicities not specified above that prolong the start of subsequent cycles by ≥ 14 days, the doses of both irinotecan and temozolomide should be reduced by 25% in the subsequent cycle. If Grade 3 or higher non-hematologic toxicity recurs or cycles are again delayed by ≥ 14 days, the patient should be removed from protocol therapy.

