9.3 Methods of Analysis

9.3.1 Primary Endpoint

The primary objective of the study is to determine the feasibility of administering 5 cycles of dinutuximab + GM-CSF and isotretinoin in combination with chemotherapy (irinotecan and temozolomide) in patients with high-risk neuroblastoma in the front-line setting following Consolidation with tandem transplant. In the absence of treatment delays, each cycle of dinutuximab-containing therapy will be completed in approximately 4 weeks, and there are 5 cycles of dinutuximab/chemotherapy-containing therapy included on this trial. Patients with disease progression detected at any time during protocol therapy or who meet pre-specified toxicity criteria will discontinue protocol-specified treatment and count against the feasibility of protocol therapy. The primary endpoint is the proportion of patients who complete 5 cycles of dinutuximab + chemotherapy without progressive disease within 30 weeks from the date of first treatment among patients who start protocol therapy.

Of the 108 patients randomized to tandem transplant on ANBL0532 that enrolled on ANBL0032 after randomization was halted, 87 (80.6%) completed at least 5 cycles of dinutuximab without progressive disease within 30 weeks. A feasibility therapy completion rate of 75% will be targeted on this study. With a sample size of 40 eligible and evaluable patients, at the 5% significance level, there will be

80% and 90% power, respectively, to detect a reduction in the therapy completion rate from target of 75% to 55.0% and 51.5%. This therapy will be declared feasible if a 95% Wilson confidence interval (CI) placed on the percentage of patients that complete at least 5 cycles of dinutuximab + chemotherapy without PD within 30 weeks contains 75% and the interim monitoring rules for feasibility and excessive toxicity (see [Section 9.3.3](#)) are not triggered. Using the closed-form formula for a 95% Wilson CI and resolving, the probability of this CI covering the value 75% when the true feasibility therapy completion rate is 50% or 60% is 0.0769 and 0.4402, respectively.

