Patients who have dose modifications but remain on therapy and are able to complete the 5 cycles without PD within 30 weeks will not count against feasibility. Patients who meet off protocol criteria due to toxicity (i.e., require greater than one dose modification for irinotecan or temozolomide, or meet off protocol criteria for dinutuximab per [Section 5.0](#)) or other criteria for removal from protocol therapy (see [Section 8.1](#)) before completion of 5 cycles will count against feasibility. Any eligible patient with prior tandem ASCT who receives at least one dose of protocol therapy will be considered evaluable for the primary endpoint.

Note: Discontinuation of isotretinoin will not count against the feasibility endpoint on this study.

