9.3.3.1 Feasibility

We will monitor for early indication of inability to administer all 5 intended cycles of dinutuximab + chemotherapy without PD within 30 weeks. Of the 108 patients randomized to tandem transplant on ANBL0532 that enrolled on ANBL0032 after randomization was halted, 89 (82.4%) completed at least 3 cycles of dinutuximab without progressive disease within 18 weeks. This feasibility monitoring rule will monitor that $\geq 75\%$ of patients will complete at least 3 cycles of dinutuximab + chemotherapy without PD within 18 weeks among patients who start protocol therapy. Patients who have dose modifications but remain on therapy and are able to complete the cycles without PD within the specified time frame above will not count against the feasibility monitoring rule.

A one-sided Pocock group-sequential boundary with a sample size of 40 will be used to monitor the number of patients that fail to receive at least 3 cycles of chemo-immunotherapy without progressive disease within

18 weeks. Interim monitoring will be done after 1/4 and 1/2 of patients have been evaluated for completion of at least 3 cycles of protocol therapy without PD (Table 3). The upper bound on the number of patients not receiving at least 3 cycles of protocol therapy without PD within 18 weeks that are needed to declare the therapy not feasible uses a cumulative alpha level of 0.125. The probability of declaring the regimen not feasible under the alternative hypothesis non-completion rates of 45% and 50% appears in Table 4. The average sample size when the non-completion rate is 25%, 45%, and 50% is 38.00, 25.32, and 20.86, respectively.

Table 3. Interim monitoring plan and number of observed patients that do not complete at least 3 cycles of chemo-immunotherapy without PD within 18 weeks needed to declare therapy not feasible.

Monitoring percent of total information	Number of patients evaluated for therapy completion	Monitoring boundary	Number of observed non-completions to declare not feasible
25%	10	1.6989 (p=0.04467)	≥ 6 (60%)
50%	20	1.6276 (p=0.05180)	≥ 9 (45%)

Table 4. Probability of detecting regimen not feasible under various alternative hypothesis therapy non-completion rates.

Monitoring percent of total information	Number of patients evaluated for therapy completion	Power under a true non-completion rate of 45%	Power under a true non-completion rate of 50%
25%	10	0.2616	0.3770
50%	20	0.5857	0.7483

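### Section 9.3.1 fails a patient who needs a second irinotecan or temozolomide modification, but Section 5.0 sets no cap across different toxicities, so one on-time completer can be scored both ways

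*Combined protocol and SAP*

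**What the plan says.** Section 9.3.1 defines the endpoint by completion, time and absence of progression: "The primary endpoint is the proportion of patients who complete 5 cycles of dinutuximab + chemotherapy without progressive disease within 30 weeks". It says that patients with dose modifications who "remain on therapy and are able to complete the 5 cycles without PD within 30 weeks will not count against feasibility". The next sentence lists those who do count against feasibility if the criterion is met before five cycles are complete: "Patients who meet off protocol criteria due to toxicity (i.e., require greater than one dose modification for irinotecan or temozolomide", or who meet the dinutuximab off-protocol criteria of Section 5.0, or another removal criterion in 8.1.

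The interim rule in 9.3.3.1 has the same allowance and no limit on the number of modifications: "Patients who have dose modifications but remain on therapy and are able to complete the cycles without PD within the specified time frame above" are not counted against it.

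Section 5.0 reduces irinotecan or temozolomide under seven rules:
- 5.1.1, neutropenia delay: patients "should have the temozolomide dose reduced by 25% for subsequent cycles".
- 5.1.2, thrombocytopenia delay: "with or without other hematologic toxicities, the dose of temozolomide should be reduced by 25% for subsequent cycles".
- 5.2.1, Grade 4 diarrhea: "the dose of irinotecan should be reduced by 25% for subsequent cycles".
- 5.2.2 (nausea and vomiting) and 5.2.3 (dehydration): both drugs cut by 25%.
- 5.2.4, liver enzymes: temozolomide cut by 25%, after a dinutuximab cut.
- 5.2.9, other non-hematologic toxicity: "the doses of both irinotecan and temozolomide should be reduced by 25% in the subsequent cycle".

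For toxicity, 8.1 refers back to Section 5.0 and adds no count. Appendix IX has one reduced temozolomide level, 75 mg/m².

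**The concern.** The limit of one modification stands in the statistical section but not in the section that tells sites when to stop treatment. A site following Section 5.0 would keep treating a patient whom 9.3.1 treats as already off protocol. If that patient finishes on time, two adjacent sentences of 9.3.1 give opposite scores. The choice between them could be made after the data are seen, and it bears on the primary endpoint. The interim rule has no cap, so the same patient can count as a completion at the interim look and a failure at the end.

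There is also a treatment gap. When a second, different toxicity calls for a temozolomide cut in a patient already at 75 mg/m², no dose is given.

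**Working it through.** **1. Can Section 5.0 lead to two cuts of one drug without removal?**

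*Same toxicity recurring.* In 5.1.1, 5.1.2, 5.2.2 and 5.2.3, recurrence after the cut means removal. In 5.2.1 a dinutuximab cut comes between the irinotecan cut and removal. In 5.2.4 the temozolomide cut is the second step, and recurrence after it means removal. 5.2.9 removes on recurrence or on a second delay of 14 days or more. No single rule cuts irinotecan or temozolomide twice, so here Section 5.0 and 9.3.1 agree.

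*Different toxicities.* The two sections part here.

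| Event | Rule | Action | Weeks |
|---|---|---|---|
| Cycle 1 | – | full dose | 0–4 |
| Thrombocytopenia, 14-day delay | 5.1.2 | temozolomide −25% | 4–6 |
| Cycle 2, Grade 3 hypokalemia | 5.2.9, first event | both drugs −25% next cycle | 6–10 |
| Cycle 3 | – | continues | 10–14 |
| Cycles 4 and 5 | – | continue | 14–22 |

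Assume no further Grade 3 or higher non-hematologic toxicity and no second long delay. Then no removal rule is met, even if the removal sentence of 5.2.9 is read broadly. Cycle 3 ends at week 14 (limit 18) and cycle 5 at week 22 (limit 30).

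A second route avoids 5.2.9: a neutropenia delay after cycle 1 (5.1.1), then severe vomiting in cycle 2 that recurs in cycle 3 despite optimized anti-emetics (5.2.2). Temozolomide is called down twice, and cycle 5 again ends at week 22.

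**2. How is this patient scored?**

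| Text | Score |
|---|---|
| Endpoint definition, 9.3.1 | success |
| Dose-modification sentence, 9.3.1 | success |
| Interim rule, 9.3.3.1 | completion |
| Parenthesis, 9.3.1 | failure |

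**3. The plan's own figures (9.3.1: n = 40, target 75%, 95% Wilson interval)**

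Wilson limits: [p̂ + z²/2n ± z√(p̂(1−p̂)/n + z²/4n²)] / (1 + z²/n), z = 1.96.
- 24/40: 44.6% to 73.7%, excludes 75%.
- 25/40: 47.0% to 75.8%, contains 75%.
- 35/40: 73.9% to 94.5%, contains 75%.
- 36/40: 76.9% to 96.0%, excludes 75%.

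The interval contains 75% for 25 to 35 completers. Summing binomial probabilities over that range gives 0.0769 at a true rate of 50% and 0.4402 at 60%, exactly as stated.

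Power by the normal approximation is Φ[(p₀ − p₁ − z·SE₀)/SE₁], with SE₀ = √(0.75×0.25/40) = 0.0685.
- p₁ = 55.0%: SE₁ = 0.0787, power 0.799.
- p₁ = 51.5%: SE₁ = 0.0790, power 0.899.

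These match the stated 80% and 90%.

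**4. Size**

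One patient is 1/40 = 2.5 percentage points. Let C be the on-time completers and k those among them with two cuts of one drug. For C between 25 and 35, the declaration is lost under the parenthesis when C − k ≤ 24. That takes k = 1 at C = 25, 2 at 26, 4 at 28 and 6 at 30.

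The documents give no rate of double cuts, so the following is an assumed range. Suppose the true rate under the endpoint definition is 75%, and a share q of all patients complete on time with two cuts. Under the parenthesis the rate is 75% − q. The probability that the interval contains 75%, ignoring the interim rules, is:

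| q | 0 | 2.5% | 5% | 7.5% | 10% |
|---|---|---|---|---|---|
| Probability | 0.958 | 0.934 | 0.882 | 0.801 | 0.694 |

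**The case against.** The strongest reply is that 9.3.1 can be read as consistent. It speaks of patients who meet off-protocol criteria, its parenthesis refers to Section 5.0, failure must arise before five cycles are complete, and its opening paragraph ties toxicity failure to stopping treatment. On this view the parenthesis is shorthand for Section 5.0's pattern of one cut and then removal.

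That may be what was meant, but the text does not say for the same toxicity. No single Section 5 rule orders a second cut of either drug. A literal second modification therefore arises only across rules, which is where Section 5.0 keeps the patient on. The qualifier about five cycles does not help, because the example patient needs the second cut before cycle 3.

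Several parts of the reply do stand:
- A reader might infer that Section 5.0 sets no limit at all. It does: each rule limits cuts for its own toxicity. Only a cap across rules is missing.
- How many rule pairs produce the conflict depends on the reading. 5.1.1 applies only when no other toxicity requires modification. 5.1.2 might be read to remove a patient already reduced for neutropenia. 5.2.9 can be read broadly. I therefore rely on the two worked examples and give no count.
- A single reduced level may mean that no second cut was intended. The text still does not say what to do instead.

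**Conclusion.** The conflict is real and minor. A patient reduced under two different Section 5 rules who completes on time is a success by the endpoint definition and a failure by the parenthesis in 9.3.1. At 25/40 one such patient decides the declaration. Further from that boundary several would be needed. The conclusion rests on Section 5.0 meaning what it says, with no unwritten cap.

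Three stronger inferences are not supported:
- *That many patients are affected.* Section 2.3 reports temozolomide modifications in 4 of 16 randomized ANBL1221 patients and does not say that anyone had two. Multiplying separate toxicity rates would not give the missing figure. The same group had Grade 3 hypokalemia in 6 of 16, so not every such event led to a temozolomide modification. The true number may be negligible.
- *That the 87/108 benchmark is mismatched because it carries no such limit.* Those patients were on ANBL0032, whose regimen as described in Section 2.2 contains no irinotecan or temozolomide, so a limit on cutting those drugs could not apply.
- *That a stated statistic is wrong.* The coverage and power figures reproduce. The problem is classification.

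**What to change.** Before analysis, choose one of two routes.

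(a) Replace the parenthesis in 9.3.1 so that failure on toxicity or removal grounds rests only on what happened to treatment: *Patients removed from protocol therapy under Section 5.0 or Section 8.1 before completing 5 cycles count against feasibility.* Keep the existing isotretinoin exception. In Section 5.0, state the dose when a second, different toxicity calls for a cut of a drug already reduced: either stay at the reduced level, or move to a second level with its own table.

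(b) If the one-reduction limit is intended, add to Section 5.0: *Irinotecan and temozolomide may each be reduced once. A patient who would require a second reduction of the same drug, for any toxicity, is removed from protocol therapy.* Carry the same wording into 9.3.1 and 9.3.3.1. This fits the single level in Appendix IX.

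Either route takes a few sentences, with no new data and no change in sample size. The price of (b) is that a few patients come off therapy, as 9.3.1 already implies. Route (a) needs a dosing decision. The removal sentence of 5.2.9 should be left alone: restricting it to recurrence of the same toxicity would, on its literal reading, loosen a removal rule, and this point does not require it.

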9.3.2 Secondary Endpoints

For event-free survival, time to event will be calculated from the time of start of protocol therapy to the occurrence of disease relapse or progression, secondary malignancy, or death. For overall survival, death will be the only event considered and time to death will be calculated from the time of start of protocol therapy. Patients without an event or death will be censored at the time of last follow-up.

9.3.3 Monitoring

Any eligible patient who receives at least one dose of protocol therapy will be considered evaluable for the monitoring rules. The study will not be halted while the data are gathered for the assessment of the monitoring rules.

9.3.3.1 Feasibility

We will monitor for early indication of inability to administer all 5 intended cycles of dinutuximab + chemotherapy without PD within 30 weeks. Of the 108 patients randomized to tandem transplant on ANBL0532 that enrolled on ANBL0032 after randomization was halted, 89 (82.4%) completed at least 3 cycles of dinutuximab without progressive disease within 18 weeks. This feasibility monitoring rule will monitor that $\geq 75\%$ of patients will complete at least 3 cycles of dinutuximab + chemotherapy without PD within 18 weeks among patients who start protocol therapy. Patients who have dose modifications but remain on therapy and are able to complete the cycles without PD within the specified time frame above will not count against the feasibility monitoring rule.

A one-sided Pocock group-sequential boundary with a sample size of 40 will be used to monitor the number of patients that fail to receive at least 3 cycles of chemo-immunotherapy without progressive disease within

18 weeks. Interim monitoring will be done after 1/4 and 1/2 of patients have been evaluated for completion of at least 3 cycles of protocol therapy without PD (Table 3). The upper bound on the number of patients not receiving at least 3 cycles of protocol therapy without PD within 18 weeks that are needed to declare the therapy not feasible uses a cumulative alpha level of 0.125. The probability of declaring the regimen not feasible under the alternative hypothesis non-completion rates of 45% and 50% appears in Table 4. The average sample size when the non-completion rate is 25%, 45%, and 50% is 38.00, 25.32, and 20.86, respectively.

Table 3. Interim monitoring plan and number of observed patients that do not complete at least 3 cycles of chemo-immunotherapy without PD within 18 weeks needed to declare therapy not feasible.

Monitoring percent of total information	Number of patients evaluated for therapy completion	Monitoring boundary	Number of observed non-completions to declare not feasible
25%	10	1.6989 (p=0.04467)	≥ 6 (60%)
50%	20	1.6276 (p=0.05180)	≥ 9 (45%)

Table 4. Probability of detecting regimen not feasible under various alternative hypothesis therapy non-completion rates.

Monitoring percent of total information	Number of patients evaluated for therapy completion	Power under a true non-completion rate of 45%	Power under a true non-completion rate of 50%
25%	10	0.2616	0.3770
50%	20	0.5857	0.7483

9.3.3.2 Excessive Toxicity

Many of the toxicities that occur due to the therapy are expected. However, we plan to consider a subset of the toxicities unacceptable. Those designated as unacceptable are listed below with the associated CTCAE v5.0 MedDRA code in parentheses:

1. Toxicity requiring the use of pressors for ≥ 24 hours, including Grade 4 capillary leak syndrome (10007196), Grade 4 anaphylaxis/allergic reaction (10002218 or 10001718) or Grade 3/4 hypotension (10021097) requiring pressors.
2. Toxicity requiring ventilatory support ≥ 24 hours, including Grade 4 respiratory toxicity such as ARDS (10001409), Grade 4 bronchospasm (10006482), Grade 4 dyspnea (10013963), Grade 4 hypoxia (10021143), Grade 4 anaphylaxis/allergic reaction (10002218 or 10001718), or Grade 4 respiratory failure (10038695) that requires intubation and mechanical ventilation.
3. Peripheral motor neuropathy Grade 4 or Grade 3 that does not resolve prior to start of next cycle of therapy (10034580).

4. Peripheral sensory neuropathy Grade 4 or Grade 3 that does not resolve prior to start of next cycle of therapy (10034620).
5. Grade 4 Cytokine Release Syndrome/Acute Infusion Reaction (10052015).
6. Toxic death.
7. Grade 4 documented infection [(infections and infestations-other, specify); 10021881].
8. Grade 4 diarrhea (10012727) that persists despite supportive care as detailed in [Section 4.2.1](#) and [Appendix V](#).

The unacceptable toxicities parallel those listed in ANBL1221 (#1-6) with the addition of documented infection (#7), as this regimen is given in the immediate Post-Consolidation setting, and diarrhea (#8) since irinotecan is included in this Post-Consolidation regimen.

There may be cause to stop the trial early if the unacceptable toxicity rate appears too high. An unacceptable toxicity rate statistically significantly >10% would be considered excessive on this trial. Of the 104 patients treated on ANBL0931 (Cycles 1, 3, 5- dinutuximab + GM-CSF + isotretinoin), the cumulative unacceptable toxicity rate for Grade \geq 4 infection (n=3) and diarrhea (n=0) was 2.9%. Among patients who received irinotecan, temozolomide and dinutuximab on ANBL1221, one had an unacceptable toxicity (Grade 4 hypoxia possibly related to therapy).

9.3.4 Assessment of Study Objectives

The primary study objective ([Aim 1.1.1](#)) related to feasibility will be assessed by estimation of the feasibility therapy completion rate together with a 95% Wilson CI. The therapy will be deemed feasible if the 95% CI placed on the percentage of patients that complete at least 5 cycles of dinutuximab + chemotherapy without PD within 30 weeks contains 75% and the interim monitoring rules for feasibility and excessive toxicity ([Section 9.3.3](#)) are not triggered.

To address Secondary [Aim 1.2.1](#), adverse events (Grade ≥ 3) experienced by patients evaluable for toxicity will be descriptively summarized.

To assess Secondary [Aim 1.2.2](#), EFS and OS Kaplan-Meier curves and estimates will be generated.

Exploratory [Aim 1.3.1](#) will be assessed by a descriptive comparison of adverse events (Grade ≥ 3) experienced by patients evaluable for toxicity according to prior anti-GD2 directed therapy (yes vs. no) status.

To address Exploratory [Aim 1.3.2](#), response will be assessed by the revised INRC²⁸ and descriptively summarized among those evaluable for response (see [Section 9.4](#)).

To address Exploratory [Aim 1.3.3](#), immune and cytokine profiles will be described at baseline and the change in immune and cytokine profiles from baseline will be descriptively summarized. There will be a descriptive comparison of the immune and cytokine profiles of those receiving chemo-immunotherapy on this pilot in the frontline setting and those receiving chemo-immunotherapy (Arm A) in the relapsed/refractory setting on ANBL1821. There will also be a descriptive comparison of immune profiles at the start and end of Post-Consolidation therapy between those who receive chemo-immunotherapy on this pilot versus standard immunotherapy on ANBL1531 (Arm A) to assess the impact of these regimens on immune reconstitution.

